Outcome measures section for more detail on the BAS3 and EYSFP). The pupil level BAS3 scores will be age-standardised with a mean of 100 and standard deviation of 15.

To address the primary research question an intention-to-treat (ITT) analysis will be undertaken using multi-level modelling (MLM) with fixed effects and random intercept. In ITT, data is analysed according to the group randomised, regardless of whether the treatment was actually received as intended, and irrespective of withdrawal from the intervention post-randomisation, or deviations in programme implementation. This principle is key in ensuring an unbiased analysis of intervention effects and is in line with the EEF's guidance (see EEF 2018).

To account for the nested nature of the data, a hierarchical linear model with two levels (school, pupil) will be fitted controlling for pre-intervention scores at the pupil level. Following the stratified randomisation, the model will include a term identifying the regions (strata).

Impact will be estimated by fitting the model in equation (1). Equation (1) is known as a 'random intercepts' model because $\beta_{0j} = \beta_0 + u_j$ is interpreted as the school-specific intercept for school j and $\beta_{0j} \sim i.i.d. N(\beta_0, \sigma_u^2)$ is random (it is a number that can take any value):

$$(1) \quad Y_{ij} = \beta_0 + IWMA_j \tau + Z_j \beta_1 + X_{ij} \beta_2 + u_j + e_{ij}$$

Where:

Y_{ij} = BAS3 scores on the number skills subtest for child i in school j ;

β_0 = the cluster-level coefficient for the slope of a predictor on number skills;

$IWMA_j$ = a binary indicator of the school assignment to intervention [1] or control [0];

Z_j = school-level characteristics i.e. the stratifying variable of geographical location (as used for randomisation);

X_{ij} = pupil level characteristics for pupil i in school j , i.e. the pre-intervention EYFSP score;

u_j = school-level residuals and

e_{ij} = individual-level residuals.

The coefficient τ in Equation 1 above will represent the outcome of the trial, with respect to the primary outcome measure. Equation 1 will also be replicated for each of the three secondary outcome measures (see next section).

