To assess whether there are systematic differences between those who drop out and those who do not – and thus whether these factors should be included in analysis – we will model missingness at follow-up (defined as pupils with missing primary outcome data at endline) as a function of baseline covariates, including treatment. The analysis model for this approach will mirror the multilevel level model specified in Equation (1), with pupils clustered in classes, but the outcome will be a binary variable identifying missingness (where 1=missing; 0=complete) in a multilevel mixed-effects logistic regression model (using Stata's `meLogit` command). We can similarly model missingness at baseline (defined as pupils with missing baseline data, namely missing EYFSP) as a function of endline covariates, including treatment.

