We will follow the protocol for missing data suggested by the EEF (see EEF, 2018). For less than 5% missingness overall from randomisation to final analysis, a complete-case analysis will be employed. This assumes that data are missing completely at random (MCAR), which we will be able to test partially with the model outlined above. For more than 5% missing data overall from randomisation to final analysis, our approach will depend on pattern of missingness. If the pattern of missingness may be unrelated to the treatment effect (e.g., pupil illness, staff changes or COVID-related impacts on testing but not on intervention), then missing data will be assumed MCAR and we will continue with a complete-case analysis. Otherwise, we will adopt a full-information maximum likelihood (FIML) approach. FIML estimates the value of the trial parameter of interest (τ in Equation 1) by maximising the likelihood function in the presence of missing data. We will not supplement this analysis with a separate approach, usually multiple imputation, MI, analysis, as the results of the two have been shown recently to be broadly equivalent (Lee & Shi, 2021). Additionally, in comparison to MI, FIML produces the same results every time, can be estimated in a single model and simulation studies show that it can reduce bias as well as MI (for a detailed discussion of FIML vs MI see Allison, 2012 or Jakobsen et al, 2017). The FIML approach only alleviates bias if pattern of missingness is dependent only on observed variables, namely missing at random (MAR); if the reason for missingness is due to unobserved variables, namely missing not at random (MNAR), then FIML or MI will not improve estimates. Note, however, that MAR and MNAR are not distinguishable based on observed data. If it seems likely data could be MNAR, sensitivity analysis will be conducted and reported alongside headline estimates.

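### The FIML fallback is set out only for Equation (1), so for pupils missing only BAS3 it returns the complete-case estimate; the baseline factors in the missingness model have no stated route into it

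*SAP*

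**What the plan says.** The SAP's Missing data section does three things.

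- **It models dropout.** Dropout is "defined as pupils with missing primary outcome data at endline". It is regressed "as a function of baseline covariates, including treatment", to see whether those lost differ systematically "and thus whether these factors should be included in analysis".
- **It sets a rule.** Below 5% missing, the analysis is complete-case. Above that, "For more than 5% missing data overall from randomisation to final analysis, our approach will depend on pattern of missingness". If missingness may be unrelated to the treatment effect, complete-case analysis stays. Otherwise FIML is used: "FIML estimates the value of the trial parameter of interest (τ in Equation 1) by maximising the likelihood function". Multiple imputation will not be run alongside, and the stated software is Stata's `sem`.
- **It says what FIML can do.** "The FIML approach only alleviates bias if pattern of missingness is dependent only on observed variables, namely missing at random (MAR". If data seem likely to be missing not at random, an unspecified sensitivity analysis follows.

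Equation (1), under Primary outcome analysis, has arm, region and one pupil-level term: "pupil level characteristics for pupil i in school j , i.e. the pre-intervention EYFSP score".

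**The concern.** The dropout model is meant to inform what enters the analysis, yet the section never says how. The only model named for the fallback is Equation (1). FIML removes bias under missing at random only when the variables that drive the missingness are in the likelihood. Baseline SNAP-IV, age, gender and FSM status are not in Equation (1).

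The FIML branch is kept for the harder case: more than 5% missing and no benign explanation. If the section is followed as written, a reader could take the FIML result as adjusted for dropout on observed characteristics when, for missing BAS3, it would be the complete-case result again. Ruling out multiple imputation as a supplement is not itself the problem, since imputation from the same variables would share the limitation.

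**Working it through.** **1. The plan's own figure.** Inputs from Table 3: 201 schools, 10 pupils each, ICC 0.16, pupil-level R² 0.25 (correlation 0.5), power 80%, two-sided alpha 5%. With 199 degrees of freedom the multiplier is 2.815. MDES = 2.815 × √(0.16 × 4/201 + 0.84 × 0.75 × 4/2,010) = 2.815 × 0.0666 = 0.188, as stated. This confirms only the design inputs; the SAP gives no figure for the missing-data question.

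**2. The identity.** For each pupil the joint likelihood is f(BAS3 | arm, region, EYFSP) × f(EYFSP | arm, region). If BAS3 is missing and the rest is observed, integrating over BAS3 turns the first factor into 1. The pupil then informs only the second factor, which does not contain τ. A school random intercept does not alter this.

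**3. Numerical check.** Trials of 201 schools × 10 pupils were simulated with ICC about 0.16 (region, always observed, was left out).

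- Only BAS3 missing, single-level FIML, 60 trials: largest difference in τ between FIML and complete case was 7 × 10⁻¹⁴.
- Only BAS3 missing, two-level random-intercept model, one trial: 0.459882 against 0.459882.
- An assumed 8% of EYFSP also missing: the estimates differ, by 0.011 in the two-level trial and by up to 0.025 in the single-level ones.

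**4. Size of the bias left in Equation (1).** Assume that dropout depends on baseline SNAP-IV. Then

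bias = r × √(0.84 × 0.75) × (difference between arms in mean SNAP-IV among tested pupils) = r × 0.794 × difference,

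where r is the within-school partial correlation of SNAP-IV with BAS3. The SAP gives no r, so 0.1 to 0.4 is assumed. With log-odds of dropout of 1 per SD of SNAP-IV in the intervention arm and random dropout in control:

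| Missing, control / intervention | Difference in mean SNAP-IV (SD) | Bias, r = 0.1 to 0.4 (SD) |
|---|---|---|
| 5% / 15% | 0.133 | 0.011 to 0.042 |
| 10% / 10% | 0.091 | 0.007 to 0.029 |
| 5% / 20% | 0.173 | 0.014 to 0.055 |

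For scale, with 9 pupils tested per school, SE(τ) = √(0.16 × 4/201 + 0.63 × 4/(201 × 9)) = √(0.00318 + 0.00139) = 0.068. The biases are 0.007/0.068 = 0.1 to 0.055/0.068 = 0.8 of an SE. The largest is 0.055/0.188 = 29% of the MDES.

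**5. Sensitivity to the mechanism.**

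- Same mechanism in both arms, 10% / 10%: difference 0, bias 0.
- Same mechanism in both arms, 5% / 15%: difference 0.133 − 0.047 = 0.086, bias 0.007 to 0.027.
- Intervention arm only, log-odds halved to 0.5, 5% / 15%: difference 0.073, bias 0.006 to 0.023.

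**6. Effect of an auxiliary variable.** In a deliberately extreme simulation (true effect 0.20, SNAP-IV slope −0.4, about 17% of BAS3 missing, dropout related to SNAP-IV in opposite directions by arm), mean τ was 0.195 with full data, 0.3155 complete-case, 0.3155 under FIML of Equation (1), and 0.195 under FIML with SNAP-IV added.

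**The case against.** The strongest reply is that the section is unfinished rather than wrong. The FIML sentence names the parameter to be estimated; it is not a list of everything in the likelihood, and nothing forbids auxiliary variables. Read with the stated purpose of the dropout model, it leaves room to carry predictors in. That stands. A reader might infer that the SAP contradicts itself, or that it rules out adding variables. The text does not support either: it asks whether factors should be included, and is then silent on how. The silence still matters, because any choice of variables would be made after the outcome data are seen.

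A reader might also infer that the fallback does nothing. It does something where EYFSP is missing. The SAP expects such gaps (pupils not assessed or exempted are recorded as A in the NPD) and plans to model them, and the 5% trigger counts missing data overall.

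Nor do the documents support a claim that the headline estimate will be badly biased. The sizes in the table need strong dropout on SNAP-IV that differs by arm, and the move from 0.195 to 0.3155 needs opposite directions by arm. Two further limits stand. The calculation does not cover loss of whole schools, which the SAP raises. And the funder guidance that the SAP follows is not at hand, so whether it addresses auxiliary variables cannot be judged.

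**Conclusion.** The concern holds in a limited form. For pupils whose only gap is BAS3, FIML of Equation (1) with no auxiliary variables is the complete-case maximum likelihood estimate. This does not depend on the assumed sizes; a complete-case fit by restricted maximum likelihood would differ only trivially. As written, then, the fallback cannot deliver the missing-at-random correction for BAS3 dropout related to SNAP-IV, age, gender or FSM status, and no stated step brings those variables in.

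The practical size is modest and rests on assumptions: 0.007 to 0.055 SD, below one SE in every scenario tabulated, under strong SNAP-IV-driven dropout in the intervention arm alone, and zero if mechanism and rate match across arms. The change is worth making because this branch is meant for the less benign dropout and the remedy is cheap.

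**What to change.** In Missing data, where FIML is adopted, state that the model for τ in Equation (1) will include a fixed, pre-specified set of auxiliary variables: baseline SNAP-IV, age in months, gender and FSM status. Observed endline PtM, working memory and SNAP-IV scores may be listed as optional auxiliaries for pupils tested on those but not on BAS3. They should be auxiliaries only, not covariates, since they are measured after randomisation. Do not add variables according to what the dropout model turns up; keep that model as description and as the partial check on missing completely at random. State that FIML of Equation (1) alone equals the complete-case estimate for pupils missing only BAS3, and report the FIML and complete-case estimates side by side.

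The cost is a few lines of text and code and a slightly larger model. Table 4 shows SNAP-IV for all 1,996 pupils (1,004 + 992), age for 1,994 (1,004 + 990) and gender for all; pupil FSM status is due from the NPD.

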IWM+A is delivered in 10 one-to-one sessions, offered in addition to dedicated numeracy lesson time, with TAs working with two pupils over the course of an hour. TAs work directly with one child for half an hour while a second child plays targeted computer games in the same room. After half an hour the children switch activities. During the one-to-one element, TAs demonstrate and practise strategies with children, which are also reinforced through adaptive online games. The children access the targeted games online with an individualised login. The WM programme is individually paced, so that each child is automatically moved to the next level of the game when appropriate, in order to keep the level of challenge suitable for each child. The arithmetic games are also self-paced but are not computer-adaptive. Children receive a record sheet that is used to record the games they played; TAs guide them when they log in to the arithmetic games.

Children only move on to the arithmetic component (+A) after participating in the WM intervention. The minimum requirements to complete the programme is for pupils to receive all five WM combined with four of the five arithmetic sessions (nine sessions in total); though five WM combined with all five arithmetic sessions is considered optimal (10 sessions in total).

This effectiveness trial encompasses two phases: a train-the-trainer phase (Phase 1), and the full implementation phase (Phase 2). In Phase 1, Oxford University trained TLs (October 2020 – July 2021). TLs attended an initial session by Oxford University in May 2020 to support TLs approach and recruit schools to the trial. The session covered an overview of the programme and the design of the trial. TLs received recruitment fliers that they were able to adapt by including their contact details and then send to schools. This was meant to be part of the TLs' training and to be followed by training sessions, but the process was interrupted after this initial session due to COVID-19.

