¹¹ There is a convention in some disciplines that a 10pp (or larger) difference in treatment and control means at baseline constitutes 'imbalance' is thus justification for including those measures in sensitivity analyses, but there are counter-arguments to this idea. See Roberts, C. and Torgerson, D. (1999) 'Baseline imbalance in randomised controlled trials', *BMJ*, 319:185; de Boer et al. (2015) 'Testing for baseline differences in randomized controlled trials: an unhealthy research behavior that is hard to eradicate', *International Journal of Behavioral Nutrition and Physical Activity*, 12:4.

The FIML approach will be implemented using the `sem` command in Stata.¹²

Compliance

As the ITT approach captures the averaged effect of *offering* the intervention, we also propose to look at treatment effects in the presence of compliance at the pupil level to capture the average effect of *participation* in IWM+A.

For the purpose of this evaluation, we are employing the EEF's definition of compliance as 'the extent to which the critical ingredients of the intervention are delivered to and/or received by the target participants' (EEF, 2019b). In collaboration with the EEF and the delivery team at University of Oxford, we have defined 'compliance' as pupil attendance at sessions, which will be collected by TAs using attendance logs using a template developed by the delivery team. TAs will be asked to share the logs with the evaluator after all sessions have been completed. As shown in Table 5, children who have attended all five WM sessions and at least four arithmetic sessions will be marked as compliant; all those that do not obtain this will be marked as non-compliant. This is in line with the expectations set-out by the project team.

Table 5. Pupil level compliance measure

Compliance criterion	Data source	Compliance indicator
Attendance at WM sessions	Register of pupil attendance recorded by TAs	Pupil has attended all five WM sessions
Attendance at arithmetic sessions	Register of pupil attendance recorded by TAs	Pupil has attended at least four out of five arithmetic sessions

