There will be two strands to the compliance analysis based on the measure outlined in Table 5. The core component of the compliance analysis will take compliance as a binary measure (where 1=compliant; 0=non-compliant, as defined Table 5), defined at the pupil level, based on attendance as recorded by the TAs. In a situation of imperfect compliance, whereby not all participating pupils are deemed compliant using the criteria outlined in Table 5, we will undertake a complier average causal effect (CACE) analysis, by drawing on an instrumental variable (IV) approach, and using a two-stage least squares (2SLS) estimation approach to recover the treatment effect for those who complied with assignment. The first stage of this approach estimates the extent to which the assignment to IWM+A encourages pupils to take up the treatment (the first stage regresses treatment assignment on compliance). This will estimate a compliance rate. Results for the first stage will report the correlation between the instrument and the endogenous variable; and an F test. The second stage of the IV estimation predicts the outcome as per Equation (1), but substitutes the treatment indicator ($IWMA_{i,t}$ in Equation (1)) with the compliance rate estimated in the first regression (Angrist & Krueger, 1991; Angrist, 2006). The results of this model will answer the research question: To what extent does *compliance with IWM+A* implementation requirements lead to improved outcomes for pupils? This model will be estimated for the primary outcome measure only.

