We are also interested in understanding the role that 'dosage' (i.e. the amount of the intervention received by pupils) has on outcomes, given the important role programme participation can have on variance in outcomes, particularly for younger children (Zhi et al., 2010). If, as measured by the binary compliance indicator described above, the non-compliance rate exceeds 10%, we therefore propose as a second additional component to the compliance analysis to include data from pupil attendance records as a more detailed categorical variable when analysing the impact of IWMA+ on the primary outcome. This variable would take on one of eleven potential categories, from 0 (indicating the pupil has not attended any IWMA+ sessions) to 10 (indicating that the pupil has attended all five WM sessions and all five arithmetic sessions) with one-unit increments. The same analytical approach will be implemented using this more detailed dosage indicator as outlined for the core compliance model above (i.e. CACE analysis drawing on an IV approach and using 2SLS estimation). This will be an additional

¹² For more information on implementing missing data analysis using the FIML approach in Stata with the `sem` command, see here <https://www.stata.com/meeting/switzerland16/slides/medeiros-switzerland16.pdf>

analysis that will sit alongside the main component of the compliance analysis to better understand how different levels of session attendance affects outcomes. As with the core compliance model, this model will be estimated for the primary outcome measure only.

The limitation to estimating a dosage-varying local average treatment effect is that no differentiation is made between compliance with working memory sessions and compliance with arithmetic sessions. That is, a student who attends five working memory sessions and no arithmetic sessions would be treated identically to a student who attends five arithmetic sessions and no working memory sessions. Whilst we recognise this limitation, we believe dosage-varying effects may be justified for exploratory analysis under a situation where there is a large degree of non-compliance (over 10%), as it seems likely that any one-on-one time with a TA, on either the arithmetic or working memory component, could improve the primary outcome and thus be partially substitutable.

Intra-cluster correlations (ICCs)

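### The binary CACE rests on an unstated assumption that the SAP's own text contradicts, and the dose model cannot show effects at different attendance levels

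*SAP*

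**What the plan says.** All of this stands in the SAP, Compliance section and Table 5, unless noted.

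- **Binary definition.** "children who have attended all five WM sessions and at least four arithmetic sessions will be marked as compliant", and "all those that do not obtain this will be marked as non-compliant". This matches the minimum programme of nine sessions in the Intervention section.
- **Estimator.** If compliance is imperfect, a CACE is estimated for the primary outcome, "using a two-stage least squares (2SLS) estimation approach to recover the treatment effect for those who complied with assignment". School assignment, one binary variable, is the instrument. The fitted value from the first stage replaces the treatment term in Equation (1). A parenthesis describes the first stage thus: "the first stage regresses treatment assignment on compliance".
- **Dose model.** If non-compliance exceeds 10%, attendance enters as a more detailed variable, called categorical, under the same approach: "This variable would take on one of eleven potential categories", from 0 to 10 in steps of one. The aim is "to better understand how different levels of session attendance affects outcomes". The one limitation admitted is that WM and arithmetic sessions are not told apart.
- **Partial attendance.** In support of the dose model the SAP argues that "it seems likely that any one-on-one time with a TA, on either the arithmetic or working memory component, could improve the primary outcome".
- **Primary analysis.** The Primary outcome analysis section specifies intention to treat, so attendance plays no part in it.

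**The concern.** An instrumental-variable CACE divides the whole effect of assignment by the share of pupils coded compliant. That is right only if assignment changes nothing for pupils coded non-compliant (the exclusion restriction). The SAP codes as untreated pupils who may have had most of the programme, and then argues that such pupils probably gain. On that argument, their gain is credited to the compliers.

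The dose model is the SAP's response to partial attendance, but one binary instrument carries one piece of information about dose. It cannot support a comparison of attendance levels.

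At stake is the answer to the SAP's named research question on compliance: what pupils gain when the programme is followed as required. The likely direction of error is upward, and nothing in the plan would warn a reader of it.

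**Working it through.** **1. Figures in the plan.** The Compliance section gives no expected compliance rate and no CACE, so there is nothing there to reproduce. The nearest design figure is the MDES of 0.188 at randomisation (Table 3). With J = 201 schools, n = 9.93 pupils, ICC 0.16, pupil-level R² 0.25 and P = 0.5:

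MDES = M·√[ICC/(P(1−P)J) + (1−ICC)(1−R²)/(P(1−P)Jn)], with M taken from t on 199 df, gives 0.1877, which agrees. It serves below only as an illustrative ITT effect.

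**2. Who is coded untreated.** There are 6 × 6 = 36 combinations of WM (0–5) and arithmetic (0–5) sessions. Only (5,4) and (5,5) are compliant; the other 34 are coded 0. These include one nine-session pattern (4 WM + 5 arithmetic) and all three eight-session patterns (3+5, 4+4, 5+3).

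**3. Size of the inflation.** Let c be the share compliant, d the share attending some sessions but falling short, and f the partial attenders' effect relative to the compliers'. The rest attend nothing. Control pupils are taken to attend no sessions: control schools are not trained, and purchase of the programme is mentioned only from September 2022, after the May 2022 endline. With the complier effect set to 1:

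- ITT = c + d·f
- binary CACE = ITT/c = 1 + d·f/c
- CACE for any session attended = (c + d·f)/(c + d)

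The SAP gives no value for c, d or f; all values below are assumptions.

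| c / d | f | Binary CACE ÷ complier effect | Any-session CACE ÷ complier effect |
|---|---|---|---|
| 80% / 15% | 0.25 | 1 + 0.0375/0.80 = 1.05 | 0.8375/0.95 = 0.88 |
| 80% / 15% | 0.75 | 1 + 0.1125/0.80 = 1.14 | 0.9125/0.95 = 0.96 |
| 70% / 25% | 0.25 | 1 + 0.0625/0.70 = 1.09 | 0.7625/0.95 = 0.80 |
| 70% / 25% | 0.75 | 1 + 0.1875/0.70 = 1.27 | 0.8875/0.95 = 0.93 |
| 60% / 30% | 0.25 | 1 + 0.075/0.60 = 1.13 | 0.675/0.90 = 0.75 |
| 60% / 30% | 0.75 | 1 + 0.225/0.60 = 1.38 | 0.825/0.90 = 0.92 |

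At f = 0 the binary CACE is exact. At f = 1 the any-session CACE is exact. For f between 0 and 1 the two bracket the complier effect.

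On the effect-size scale, an ITT effect of 0.188 gives a binary CACE of 0.188/0.80 = 0.235 at 80% compliance and 0.188/0.70 = 0.269 at 70%.

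**4. How strict the threshold is.** Suppose attendance is independent across sessions, with probability 0.95 each, and the effect is linear in sessions (both assumed). The compliant share is 0.95⁵ × (0.95⁵ + 5 × 0.95⁴ × 0.05) = 0.774 × 0.977 = 0.76. In simulation, non-compliers average 8.6 sessions and the ratio is 1.28.

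**5. Dose model.** Two readings are possible.

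- *Ten indicators for 1 to 10 sessions.* There are ten endogenous terms and one excluded instrument. In a numerical check, the fitted second-stage matrix with a constant had rank 2 where 11 is needed. The model is not identified.
- *One numeric score from 0 to 10.* The rank is 2 where 2 is needed, so the model is just-identified. It yields one number, an average effect per session, which extrapolates to the full programme only under linearity.

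Interactions of assignment with region could add instruments, but the SAP does not plan them.

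**The case against.** The strongest case on the other side is that this is a supplementary analysis with an agreed definition and some loose wording. Several stronger readings are tempting and should be set aside.

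- **That the trial's headline effect is overstated.** The primary analysis is ITT and does not use the compliance variable.
- **That the CACE certainly overstates.** It does so only if partial attenders benefit. The SAP says that this seems likely, not that it is known. If f = 0 the ratio is 1.00.
- **That the dose model is unidentifiable however it is read.** The SAP describes a single variable in unit steps replacing a single term, which can be read as a numeric score, and that is identified. What stands on both readings is that level-specific effects are out of reach.
- **That the first stage will be run backwards.** The same sentence says that it measures how far assignment encourages take-up, and the next that it yields a compliance rate. The parenthesis is a slip.
- **That clustering is ignored.** The second stage refers to Equation (1), which contains the school residual, and the Effect size calculation section promises an interval that allows for clustering. What remains unspecified is the first-stage covariates, whether the stages are estimated jointly, and how the standard errors are obtained.
- **That the 10% trigger is a fault.** With non-compliance at or below 10% and f no greater than 1, the ratio cannot exceed 1 + 0.10/0.90 = 1.11. The trigger is defensible.
- **That dose should replace the binary analysis.** The binary definition was agreed with the funder and the delivery team. A numeric dose has its own bias if linearity fails. With c = 70%, d = 25%, f = 0.75, compliers attending ten sessions and partial attenders five (assumed), ten times the slope is 0.8875/0.825 = 1.08 times the full-programme effect.

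None of this removes the core: the exclusion restriction is not stated, and the SAP's own argument runs against it.

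**Conclusion.** The point holds for the secondary compliance analysis. The binary CACE needs an assumption that the SAP omits and elsewhere argues against. If partial attenders gain in the same direction as compliers, the estimate is biased away from zero, by a factor of 1.05 to 1.38 over the assumed attendance rates and f from 0.25 to 0.75. The actual size cannot be known from the SAP, because attendance and partial effects are not given. The dose model, on either reading, cannot deliver its stated aim; at best it gives an average per-session effect. The ITT result stands as planned. This should be corrected before analysis, but it does not threaten the trial's main conclusion.

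**What to change.** In the SAP, Compliance section:

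1. Keep the agreed binary CACE as the core analysis. State the exclusion restriction, and say that the estimate is likely to be an upper bound if partial attendance helps.
2. Add a CACE with compliance defined as any session attended. Present the two as a bracket, valid if partial attenders gain between nothing and the full complier effect.
3. Define dose as a single numeric variable from 0 to 10, with control pupils at 0. Report it as an average per-session effect under a stated linearity assumption, and delete the aim of effects by attendance level.
4. Reword the first stage as compliance regressed on assignment, with the Equation (1) covariates (strata and EYFSP). State that both stages are estimated jointly with school-clustered standard errors.

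The cost is wording and one extra instrumental-variable run on attendance logs already planned, plus assumptions that must be stated openly. Running the dose model whatever the level of non-compliance, or making it the main compliance model, is a matter of preference and is not needed.
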